2.1 Trial Design

This is a 2-part prospective trial examining the ability of Stereotactic Body Radiation Therapy (SBRT) to induce a response to MK-3475, a humanized antibody to PD-1, in patients who progress on this antibody. Patients with metastatic melanoma and NSCLC will be enrolled after they have progressed on anti-PD-1 therapy. Patients with metastatic NSCLC (previously untreated with anti-PD-1 or anti-PD-L1 therapy) will be enrolled and treated with MK-3475 until they exhibit progression of disease (as defined in section 5.2.1). At this point (when patients have demonstrated progression of disease) a single target lesion will be selected and treated with SBRT, and then MK-3475 will be restarted and continued until there is further progression of disease. The first phase of the study is a radiation dose escalation with a constant dose of MK-3475. The second part of the study includes an expansion cohort of NSCLC patients.

The phase 1b portion of the trial is a radiation dose escalation study to determine the maximum tolerated dose (MTD) of SBRT when given to patients previously and subsequently exposed to anti-PD-1 therapy, including MK-3475. Because the class of PD-1 inhibitory antibodies conveys a risk of pneumonitis, there will be two parallel dose escalation arms- Arm A will include SBRT targets in the lung parenchyma, and Arm B will be limited to targets outside the lung parenchyma. Each arm will be separately escalated, and two MTDs will be determined. The starting dose will be 3000 cGy in 5 fractions; there will be one dose escalation cohort (3000 cGy in 3 fractions), and if necessary one dose de-escalation cohort (1000 cGy in a single fraction). If there is dose-limiting toxicity at the lowest cohort, that arm will be closed and SBRT to that site will be discontinued.

The phase 2a portion of the study includes an expansion cohort for NSCLC, with SBRT delivered at the MTD. The primary endpoint of this phase of the study is the overall response rate to post-SBRT MK-3475. Secondary endpoints include determining the time to progression, overall survival, and exploratory biomarkers.

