3.2 Secondary Objectives

- (1) To determine the local control of SBRT, when SBRT is given with MK-3475
- (2) To determine the time to progression in patients receiving post-radiation MK-3475, in patients whose disease had previously progressed on MK-3475 or another anti-PD-1 therapy.
- (3) To determine the progression-free and overall survival in patients receiving MK-3475, who receive SBRT
- (4) To determine the safety and toxicity of the combination of SBRT and MK-3475
- (5) To examine potential predictive biomarkers in tumor samples and peripheral blood in patients treated with MK-3475 and SBRT.

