Following SBRT, MK-3475 will be re-started and administered in 3-week cycles as quickly as feasible. Dose modifications or delays may be made per section 5.2.2, based on prior toxicity from the first course of drug treatment. Treatment will continue until progression of disease, which **will be defined for this purpose as progression in comparison to the tumor imaging obtained immediately before or after SBRT (whichever is more recent)**. At the discretion of the principal investigator, patients may continue to receive treatment if they are receiving clinical benefit. For the purpose of measuring response, the irradiated lesion will no longer qualify as measurable disease.

Progression of Disease (irPD) for this study will be defined using the Immune-Related Response Criteria (irRC), with the following qualification:

Radiographic progression of disease by RECIST criteria (but not by irRC) where, in the opinion of the investigator, the patient would no longer benefit from continuing drug therapy, will be considered progression of disease.

During the **pre-SBRT** MK-3475, radiation to isolated sites of metastatic disease is not permitted.

During the **post-SBRT** MK-3475, local surgery and/or radiation therapy to isolated sites of metastatic disease is permitted and the patient can continue the MK-3475 provided there is evidence of continuing benefit from systemic treatment (i.e., stable disease or response in at least one other measurable lesion, or clinical improvement).

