5.7 Subject Withdrawal/Discontinuation Criteria

Subjects may withdraw consent at any time for any reason or be dropped from the trial at the discretion of the investigator should any untoward effect occur. In addition, a subject may be withdrawn by the investigator if enrollment into the trial is inappropriate, the trial plan is violated, or for administrative and/or other safety reasons. Specific details regarding discontinuation or withdrawal are provided in Section 7.

A subject must be discontinued from treatment, or removed from the study for any of the following reasons:

- The subject or legal representative (such as a parent or legal guardian) withdraws consent.
- Progression of disease during the second course of MK-3475 (as defined in section 5.2.1)
- Unacceptable adverse experiences as described in Section 5.2
- Intercurrent illness that prevents further administration of treatment
- Investigator's decision to withdraw the subject
- The subject has a confirmed positive serum pregnancy test

- Noncompliance with trial treatment or procedure requirements
- The subject is lost to follow-up
- Completed 12 months of treatment with post-SBRT MK-3475
Note: 12 months of study medication is calculated from the date of first dose of the second course. Subjects who stop MK-3475 after 12 months will be eligible for up to one year of additional study treatment if they progress after stopping study treatment
- Administrative reasons

The End of Treatment and Follow-up visit procedures are listed in Sections 6 and 7. After the end of treatment, each subject will be followed for 30 days for adverse event monitoring (serious adverse events will be collected for 90 days after the end of treatment as described in Section 8). Subjects who discontinue treatment will be followed for survival until death, withdrawal of consent, or the end of the study, whichever occurs first. Survival follow up may be a phone call only.

58 Subject Replacement Strategy

In both phases of the study, patients will be replaced if

1. They do not complete at least one fraction of SBRT.
2. They do not complete their entire course of SBRT as prescribed due to reasons other than toxicity (e.g., patient refusal, or intercurrent illness).

59 Clinical Criteria for Early Trial Termination

Early trial termination will be the result of the criteria specified below:

1. Quality or quantity of data recording is inaccurate or incomplete
2. Poor adherence to protocol and regulatory requirements

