The primary endpoint of this trial will be response rate and the secondary endpoint will be progression-free survival. We will use descriptive statistics to calculate frequency and proportion for the response rate to post-SBRT MK-3475. 95% confidence interval will also be provided. Exact binomial test will be used to compare the observed response rate versus historical control. For the secondary endpoint, we will use Kaplan-Meier estimator to present the progression-free survival.

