12.2 Progression-Free and Overall Survival

For the purpose of the secondary endpoints of this study, PFS is defined as the time from initiation of study drug post-SBRT, until the first documented, confirmed progression of disease as described in Section 5. PFS will also be measured and report from the initiation of study drug, pre-SBRT. OS will be measure from the initiation of study therapy.

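### Section 12.2 gives PFS one end event, confirmed progression, so a patient who dies without documented progression is censored and the curve reported as PFS is time to progression

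*Combined protocol and SAP*

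**What the plan says.** Section 12.2 gives the definition: "PFS is defined as the time from initiation of study drug post-SBRT, until the first documented, confirmed progression of disease", with progression taken as Section 5 describes it. It adds a second PFS measured from the start of study drug before SBRT and gives no separate end event for that clock.

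Section 5.2.1 defines progression as irPD under irRC, with one qualification that opens "Radiographic progression of disease by RECIST criteria (but not by irRC) where, in the opinion of the investigator" and covers patients judged unlikely to gain from more drug. Both routes rest on imaging, and neither includes death.

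The endpoints are named in three places:

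- Section 2.1: "Secondary endpoints include determining the time to progression, overall survival, and exploratory biomarkers".
- Section 3.2, objective (2): "To determine the time to progression in patients receiving post-radiation MK-3475". Objective (3): "To determine the progression-free and overall survival in patients receiving MK-3475, who receive SBRT".
- Section 9.0: "The primary endpoint of this trial will be response rate and the secondary endpoint will be progression-free survival".

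For PFS, Section 9.0 specifies a Kaplan-Meier estimate. It lists no events and no censoring rule. Section 7.4 provides for survival contact every 12 weeks after treatment ends.

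**The concern.** PFS is normally the time to progression or death, whichever comes first. An endpoint that stops only at progression is time to progression, and the two differ in how they treat a patient who dies first. Under 12.2 that patient has no event, so the follow-up is censored. Kaplan-Meier then treats the patient as someone who could still have progressed later, at the same rate as those who remain at risk. These are among the worst outcomes in the cohort, so removing them from the events can only raise the curve.

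Section 3.2 intends two quantities. With the end event in 12.2, PFS and time to progression after SBRT would be the same number, and a reader of the trial report would take the figure labelled PFS to include deaths.

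**Working it through.** **Is death an event anywhere?** Section 12.2 names one end event and refers to Section 5. Section 5.2.1 offers two routes to progression, irPD or RECIST progression with the investigator's judgment, and death is in neither. Section 9.0 names the estimator only. No other section adds death, so a literal reading censors it.

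**Is time to progression defined elsewhere?** No. It appears in 2.1 and 3.2, but 12.2 covers only PFS and OS, and 9.0 does not mention it.

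**Size.** The plan bases no sample size, test or threshold on PFS, so there is no stated figure to reproduce. The following is an illustration on assumed inputs.

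- m = true median PFS with deaths counted, assumed 12 weeks.
- f = share of first events that are deaths without documented progression, assumed 5%, 10% or 20%.
- Constant hazards.

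With deaths counted, S(t) = 0.5^(t/m). With those deaths censored, the curve becomes S(t)^(1−f).

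Week 24 is a suitable time to read it, because 8 cycles × 3 weeks = 24 weeks is a scheduled scan. There S(24) = 0.5^(24/12) = 0.250.

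| f | Calculation | 24-week PFS under 12.2 | Excess, patients of 20 |
|---|---|---|---|
| 5% | 0.25^0.95 | 26.8% | 0.4 |
| 10% | 0.25^0.90 | 28.7% | 0.7 |
| 20% | 0.25^0.80 | 33.0% | 1.6 |

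If m is 24 weeks instead, S(24) = 0.500 becomes 51.8%, 53.6% and 57.4%.

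**Is 5% to 20% a plausible range?** Post-SBRT scans fall at the end of cycles 2, 4, 8, 12 and 16, nominally weeks 6, 12, 24, 36 and 48. Suppose progression occurs at rate L = ln2/12 per week, and death after progression at rate M = ln2/(median survival after progression). The chance of progressing in a scan interval (a, b) and dying before the scan at b is the integral from a to b of L·exp(−L·u)·(1 − exp(−M·(b−u))) du. Summing over the intervals to week 48:

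| Assumed median survival after progression | Dead before documentation | As share of first events | Kaplan-Meier at week 24 (true 25.0%) |
|---|---|---|---|
| 52 weeks | 1.1 of 20 | 6% | 26.7% |
| 26 weeks | 2.2 of 20 | 12% | 28.5% |
| 13 weeks | 4.0 of 20 | 22% | 32.0% |

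This model allows no scans prompted by symptoms, which Section 12.0 permits and which would lower the share. Deaths unrelated to progression would raise it. It shows that the range is reasonable; it does not estimate what will happen in this trial.

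**The case against.** The strongest reply is that 12.2 omits death and does not exclude it. PFS has a settled meaning, 3.2 separates it from time to progression, and an analyst could apply the usual convention. That is a fair guide to what was probably intended. But 12.2 does state an end event, and only one, so counting deaths means departing from the written definition. That choice is better settled in the text before the data are seen.

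A second reply is that the effect is small and assumed. This stands. At f = 10% the shift is under one patient in 20, while the exact 95% interval for 5 of 20 runs from about 9% to 49%. No test or decision depends on PFS.

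The documents do not support several stronger readings that a reader might infer:

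- **That 2.1, 3.2 and 9.0 contradict one another on the endpoint.** Section 3.2 lists both endpoints, and the list in 2.1 is not exhaustive. Section 9.0 is narrower, but it also leaves out OS and local control and reads as a summary.
- **That confirmation of progression is impossible or undefined.** Section 5.2.1 adopts irRC by reference, so the absence of a confirmation step in the protocol text does not show that none applies. Section 5.2.1 also lets drug continue for clinical benefit, with its cycle-based scans.
- **That progression cannot be detected once drug stops.** Sections 7.5 and 12.0 allow extra imaging, and the note in 5.7 on re-treatment expects progression after stopping to be found.
- **That PFS should be read only to week 48.** That would be a preference. Dosing windows and holds mean that cycle 16 does not fall at a fixed week.

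**Conclusion.** The point holds in a narrow form. As written, the PFS rule in 12.2 censors deaths without documented progression, and the resulting curve is time to progression, biased upward. The direction follows from the definition. The size does not come from the documents: 27% to 33% in place of 25% at 24 weeks rests on an assumed 12-week median, an assumed 5% to 20% share of such deaths, and constant hazards. The response-rate endpoint, the 4-of-20 rule and the sample size are unaffected. Severity is minor.

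The second PFS clock has a related gap. Patients who start MK-3475 on trial receive SBRT only after progressing. If that progression counts, the clock ends before SBRT for every one of them; if it does not, the end event is a later progression. Section 12.2 does not say which is meant.

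**What to change.** Replace the PFS definition in 12.2 with wording to this effect:

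- **PFS:** time from the first post-SBRT dose of MK-3475 to the first documented progression as defined in 5.2.1 or death from any cause, whichever comes first. Patients alive without progression are censored at their last tumor assessment.
- **Time to progression:** same start, with deaths without documented progression censored.
- **PFS from pre-SBRT drug start:** count death as an event, and state whether the progression that leads to SBRT ends the clock.

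In 9.0, name both PFS and time to progression as secondary endpoints.

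The cost is wording only. OS is already a secondary objective and survival is already followed every 12 weeks, so the change needs no new visit, scan, data field or patient.

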5.2.1 Study Design

This is a two-part study, including both phase 1b and 2a portions.

The **phase 1b** is an SBRT dose escalation study, in which patients with both NSCLC and melanoma will be enrolled. NSCLC patients will be enrolled and treated with MK-3475 until they have progression of disease (irPD). Patients who have progression within 12 months of study entry will be evaluated for SBRT and re-initiation of MK-3475. Patients who do not have progression of disease within that timeframe may continue to receive MK-3475 for up to 18 months per protocol. These patients will not be evaluable for the study endpoints, although their response rates and overall survival will be reported.

Melanoma and selected NSCLC patients will be enrolled after having progression of disease on prior PD-1 therapy (irPD). They will be immediately treated with SBRT, followed by re-initiation of MK-3475.

After progression of disease on an initial course of anti-PD-1 therapy (either prior to enrollment, or during trial therapy), a target for SBRT will be selected and patients will be assigned to one of two arms on the basis of the anatomic location of the target (Arm A: lung, Arm B: non-lung). The SBRT target will be chosen and ideally SBRT will be delivered as quickly as feasible after the last infusion of MK-3475. NSCLC patients who do not have a suitable SBRT target (as defined in section 5.2.3) on the imaging study that shows progression of disease may undergo interval re-imaging without further therapy, but if no suitable target has been identified for SBRT within 12 weeks of the last infusion of MK-3475, that patient will be removed from treatment and moved to survival follow up.

Patients may continue to receive MK-3475 post disease progression while radiation therapy with SBRT is scheduled. Patients who require continuing corticosteroid treatment, or who have adverse events (grade 3 or greater non-hematologic, or grade 2 pneumonitis) due to MK-3475 that do not resolve within 12 weeks of AE start date will not receive SBRT and will also be removed from study. Patients who develop grade 3 pneumonitis will be removed from the study, regardless of whether it resolves. SBRT will be delivered in dose cohorts as described below in section 5.3.

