5.2.3 Stereotactic Body Radiation Therapy (SBRT)

Target Selection

Target selection for SBRT will occur after the patient develops progression of disease on the pre-SBRT treatment with MK-3475. For the Phase Ib portion, patients will be allocated to Arm A (Lung target) if the SBRT target overlaps the lung parenchyma, otherwise patients will be allocated to Arm B (Non-Lung target). Targets suitable for SBRT for all phases of the study must meet all of the following requirements. Melanoma and NSCLC patients with prior treatment on anti-PD1 therapy will only be enrolled if there is a suitable target. In NSCLC patients initiating MK-3475 as first protocol treatment, if there are no suitable targets for SBRT after the pre-SBRT MK-3475, the patient may be observed and interval re-imaging may be obtained at the discretion of the investigators. Patients who cannot be treated with SBRT within 12 weeks of the most recent infusion of MK-3475 will be taken off treatment and moved to survival follow up. Exceptions to the 12 week window may be allowed for individual patients at the discretion of the Principal Investigator. MK-3475 may be administered after progression has been determined while SBRT is planned. Additionally, target lesions:

1. Must not be located in the liver, small or large bowel
2. Treatment must be accomplished without exceeding any normal tissue dose limit, as defined in the report of the American Association of Physicists in Medicine, Task Group 101 report[55].

SBRT Planning

Patients will undergo CT simulation and treatment planning per standard practice. Patient immobilization should be sufficient to ensure minimal intra- and inter-fraction set-up error, and is otherwise left to the discretion of the treating radiation oncologist. For lung targets, a technique for motion management is required, which may include tumor tracking, respiratory gating, or 4D-CT simulation. The treating physician will define a planning target volume (PTV) to which the dose will be described, and which will be used to define local control or local failure. At least 90% of the PTV should receive 90% or more the prescription dose. All organs at risk within 5 cm of the PTV will be contoured, and dose-volume histograms produced. For all organs at risk contoured, dose limits will be followed without exception[55].

SBRT Treatment Administration

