6.0 STUDY CALENDAR – NSCLC PATIENTS WITHOUT PRIOR ANTI-PD-1 THERAPY

Trial Period:		Treatment												End of Treatment		Follow Up	
Treatment Cycle/Title:		Screening	1	2	3+	4+	At Progression ¹⁰	SBRT	1	2	3+	4+	At Progression, Discontinuation	Safety Follow-Up	Survival Follow-up		
Scheduling Window (Days):	-28 to -1	± 7	± 7	± 7	± 7	± 7	± 7		± 7	± 7	± 7	± 7	± 7	30 Days post End of Treatment (± 7)	Every 12 weeks (± 7)		
Informed Consent	X																
Medical History	X																
Full Physical Exam, VS & weight	X																
Height	X																
Medication Review	X	X	X	X	X	X	X		X	X	X	X	X				
CT chest/abdomen/pelvis ¹	X		X		X				X		X		X				
Directed Physical Exam, VS & weight		X	X	X	X	X	X		X	X	X	X	X				
ECOG Performance Status	X	X	X	X	X	X	X		X	X	X	X	X				
Adverse Event Assessment	X	X	X	X	X	X	X ³	X	X	X	X	X	X	X ¹⁴			
Pregnancy Test – Urine or Serum β-HCG	X ¹¹																
Archival or Fresh Tumor Collection ⁴	X ²																
CBC with Differential	X	X	X	X	X				X	X	X	X					
CMP, LDH	X	X	X	X	X				X	X	X	X					
TSH & Free T4 ¹⁵	X		X		X				X		X						
Selection of SBRT target ⁷						X											
Blood for correlative studies	X ^{5, 12}	X ^{5, 12}	X ⁵	X ⁵	X ⁵	X ⁵	X ⁵	X ^{5, 12}	X ^{5, 12}	X ⁵	X ⁵	X ⁵	X ⁵				
Survival follow-up															X		
Administer study drug, MK-3475 ⁹			X ¹¹	X	X	X ^{6, 13}			X ⁸	X	X	X ¹⁶					

¹ During week 3 every 2 cycles (during the last week of cycles 2 and 4), and then every 4 cycles (at the end of cycles 8, 12, etc.). See Section 8.5 for exceptions.

² Includes PD-L1 testing

³ Study visit the last day of SBRT

⁴ When feasible, if a biopsy is done for clinical purposes as per standard of care at any point during a subject's participation on trial, tissue may be collected at the time of the biopsy

⁵ Blood for correlative studies will be drawn at cycles 2 through 4 for both pre- and post-SBRT, then every even-numbered cycle thereafter (e.g. 6, 8, 10, etc.). If MK-3475 is held for any reason when blood for correlative samples is to be drawn, the blood may be drawn at the discretion of the Principal Investigator. When MK-3475 is resumed, blood for correlative samples will be taken as per the calendar above.

⁶ May be administered for up to 18 months if no disease progression. If no disease progression and > 12 months on study drug, patient cannot receive SBRT on trial

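### OS for patients who receive SBRT is timed from the start of study therapy, so PD-1-naive NSCLC patients carry guaranteed pre-SBRT survival time that pretreated patients do not

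*Combined protocol and SAP*

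**What the plan says.** Objective 3 in section 3.2 reads "To determine the progression-free and overall survival in patients receiving MK-3475, who receive SBRT". Section 12.2 defines the only OS clock: "OS will be measure from the initiation of study therapy". PFS, by contrast, has two clocks there. The main one starts at the post-SBRT restart of study drug, and a second is described as "PFS will also be measured and report from the initiation of study drug, pre-SBRT".

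Patients reach SBRT by two routes (section 5.2.1):

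- **PD-1-naive NSCLC.** "NSCLC patients will be enrolled and treated with MK-3475 until they have progression of disease (irPD"). SBRT comes afterwards: "Patients who have progression within 12 months of study entry will be evaluated for SBRT and re-initiation of MK-3475". The first study calendar (6.0) sets the same limit: "If no disease progression and > 12 months on study drug, patient cannot receive SBRT on trial". Section 5.2.3 adds a time window: "Patients who cannot be treated with SBRT within 12 weeks of the most recent infusion of MK-3475 will be taken off treatment".
- **Melanoma and NSCLC with prior anti-PD-1 therapy.** "They will be immediately treated with SBRT, followed by re-initiation of MK-3475".

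The phase 2a text in 5.2.1 admits NSCLC patients by either route. Section 9.0 names Kaplan-Meier for PFS only. It gives no method, landmark, delayed-entry handling or split by route for OS. Patients who do not progress on the first course are not evaluable for the study endpoints, although their OS will be reported (5.2.1).

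**The concern.** Membership of the objective 3 population depends on a later event, receipt of SBRT. On the naive route the OS clock starts before that event. A naive patient who dies before SBRT never enters the population, so every naive patient who does enter was certain to survive the lead. This is immortal time, and it lengthens OS whatever SBRT does.

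The lead is close to zero on the other route. A summary over both routes therefore moves with the share of naive patients and with the length of their first course. Restricting to NSCLC does not remove the mixture, because both routes feed that cohort.

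The trial has one arm, so its OS estimate will be read on its face or against outside figures. The bias is in the favourable direction.

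**Working it through.** The documents state no OS target, event count or power, so there is no planned figure to reproduce. The check has three steps.

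**1. When the clock starts relative to SBRT**

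| Route | First study therapy | OS origin relative to SBRT |
|---|---|---|
| PD-1-naive NSCLC | MK-3475 until progression | Before SBRT, by the whole first course plus the wait |
| Melanoma, pretreated NSCLC | SBRT, then MK-3475 | At SBRT, or just after it if study therapy is read as study drug |

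**2. Length of the lead on the naive route, from the protocol's own windows** (1 month = 365.25/12 = 30.44 days)

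- Nominal longest: 12 months + 12 weeks = 12 + 84/30.44 = 12 + 2.76 = 14.8 months.
- If the last infusion was one 3-week cycle before progression: 12 + 63/30.44 = 14.1 months.
- Progression at the first scheduled scan (end of cycle 2): 42/30.44 = 1.4 months.

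The 14.8 months is not a cap. Drug may continue after progression while SBRT is arranged, which moves the 12-week window, and section 5.2.3 allows exceptions to that window.

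**3. Effect on the OS median (illustration; these inputs are assumptions, not document figures)**

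Assume post-SBRT survival is exponential with median m. Assume the time R to first progression is exponential with median 3 or 6 months, truncated at 12 months because later progressors do not get SBRT. Assume 1 month from progression to SBRT. Then OS on the protocol clock = R + 1 + post-SBRT survival on the naive route, and post-SBRT survival alone on the other route.

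The truncated median of R solves 1 − 2^(−t/r) = ½(1 − 2^(−12/r)):

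- r = 3: the right side is 0.469, so t = 2.7 months and the lead is 2.7 + 1 = 3.7 months.
- r = 6: the right side is 0.375, so t = 4.1 months and the lead is 4.1 + 1 = 5.1 months.

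A typical lead under these assumptions is therefore about 4 to 5 months, roughly a third of the nominal longest. Medians of the resulting OS distribution, in months:

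| True post-SBRT median | Naive route reads | 50:50 mix reads |
|---|---|---|
| 6 | 11.0 to 12.3 | 8.7 to 9.4 |
| 9 | 13.9 to 15.1 | 11.6 to 12.4 |
| 12 | 16.8 to 18.0 | 14.6 to 15.3 |

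The ranges run from r = 3 to r = 6. At a true median of 9 months, 12-month OS after SBRT is 2^(−12/9) = 40%. On the protocol clock it reads 58 to 63% on the naive route and 49 to 52% in the mix.

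The size depends on the assumed lead. With a lead spread uniformly from 1.4 to 14.8 months, the 50:50 mix at a true median of 9 months reads 14.0 instead of 11.6 to 12.4. The direction is the same.

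**The case against.** **The OS population is not named in 12.2.** OS from first dose in every patient who starts treatment is a conventional analysis with no immortal time. Section 7.4 follows everyone who stops therapy for survival, and 5.2.1 promises OS for patients who never progress. This is the strongest defence. But objective 3 restricts OS to SBRT recipients, 5.2.1 calls the non-progressors not evaluable for the study endpoints, and 5.8 replaces anyone without a fraction of SBRT. If all starters were meant, 12.2 and objective 3 conflict and the text still needs changing.

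**Consequence is limited.** This stands. OS is secondary and descriptive, no OS test or decision rule exists, and the main PFS clock already gives a time-to-event result that starts after SBRT.

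A reader might infer three stronger points, which the documents do not support:

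- *That one pooled OS curve is planned.* No OS curve of any kind is specified in section 9.0. The mixing of origins applies to any summary that combines the routes; it is not a stated plan to combine them.
- *That PFS from the pre-SBRT start must fall to zero by month 12.* That would hold only among naive SBRT recipients with first progression as the event. Section 12.2 does not restrict this PFS to SBRT recipients, and its natural population is everyone who starts the first course.
- *That the main PFS clock is also wrong.* It starts at the post-SBRT restart of drug on both routes and fits the stated interest in post-radiation MK-3475. No defect is shown.

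**Conclusion.** The OS rule is wrong as written for objective 3. Its only clock starts before SBRT on one route and at or after SBRT on the other, while the objective concerns SBRT recipients. On the naive route it adds survival time that selection guarantees, so the bias in OS is upward.

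The direction follows from the documents alone, given the population in objective 3. The size does not. The windows give a nominal longest lead of 14.8 months, and the 4 to 5 month typical lead and the shifted medians rest on the assumed run-in, delay, mix and exponential survival. The fault concerns the meaning of a descriptive secondary estimate. The primary response endpoint, the 4-of-20 rule and the main PFS clock are not affected.

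**What to change.** In section 12.2:

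1. For objective 3, measure OS from the first SBRT fraction in all patients who receive SBRT, on both routes.
2. Separately, report OS from the first MK-3475 dose in all PD-1-naive NSCLC patients who start it, whether or not they reach SBRT. Use the same population for the PFS measured from pre-SBRT study drug.
3. Leave the main PFS clock, from the post-SBRT start of study drug, as it is.

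The cost is a wording change. Treatment dates and the 12-weekly survival follow-up already supply the data, and no visit, patient or sample size changes. The downside for the sponsor is that the OS figure for SBRT recipients becomes less favourable.
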